9.4 STATISTICAL ANALYSES

9.4.1 GENERAL APPROACH

Descriptive statistics will be used to characterize the overall cohort and each facility cohort for the variables of interest. Summary statistics will include means with standard deviations for normally distributed data and medians with interquartile ranges for skewed data. Categorical data will be summarized with frequencies and percentages. All tests will be two-sided and conducted at $\alpha=0.05$ and all confidence intervals calculated at 95% unless otherwise stated. All variables for the primary analyses are stated below. Although we will assess normality assumptions for the primary and secondary outcomes, we do not plan to use transformations for these scale outcomes due to lack of interpretability and the large sample size of the trial providing robustness to normality deviations in estimating and testing intervention effects. A full Statistical Analysis Plan is available as a separate document (HearCARE Statistical Analysis Plan, October 6, 2021).

9.4.2 ANALYSIS OF THE PRIMARY ENDPOINT(S)

We will use linear mixed models to test the hypothesis of improving satisfaction with participation and hearing-specific HRQoL specifying the fixed effects of intervention and time and random effects for facility, facility*time, and resident (**RC-4**). These random effects are based on the statistical model referenced in Hooper (2016)⁸¹ that account for the correlation among individuals in the same cluster at the same time point, correlation between observations for the same individual at two time points, and the correlation between two means of the same cluster at two time points. Time will be treated as a categorical variable. We will estimate the mean difference and corresponding 95% confidence interval for the intervention effect (**IR-1**) and test that the difference between intervention and control conditions is significant. A two-sided test $\alpha=0.025$ for each outcome using a Wald t-test with Kenward Roger correction for small sample bias and Satterthwaite degrees of freedom will be employed. Primary analysis will be unadjusted for covariates.

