being continuously followed (**CI-2**). We expect some residents to leave the facility for different reasons and our design will allow new residents to contribute data from the time of moving into the facility until the end of the study period. We conducted sample size analyses accounting for intracluster correlation ($\rho=0.20$) (**RC-3**), individual autocorrelation ($\tau=0.5$), and cluster autocorrelation ($\pi=0.9$)⁸⁴. The *intracluster correlation* is a measure of correlation among residents measured at the same facility within the same time frame. Cluster randomized trials typically assume values between 0.01-0.10 with higher values indicating more similarity in outcomes within clusters such as schools, primary care clinics, or providers. We assumed a higher correlation given that residents are living within the same quarters and sharing the same residential experience. The *individual autocorrelation* is the correlation between any two measures within the same resident over time. We conservatively assumed this to be 0.5 as a lower bound because repeated measures within person are often highly correlated. The *cluster autocorrelation* is the correlation between two population means from the same cluster at different times. We assumed this would be very high (0.9) given the stability of the population in the facilities over time. This design achieves 80% power to detect the hypothesized effect size of 0.3 for either primary outcome (satisfaction with participation or hearing-specific health-related quality of life) between control and intervention periods (two-sided, $\alpha=0.025$ for each outcome). An effect size of 0.3 translates to a difference between groups of 3 points on the satisfaction with communication scale assuming a standard deviation between 9 and 10 based on our preliminary data from local facilities. An effect size of 0.3 translates to a difference between groups of 3.6 points on the hearing-specific health-related quality of life measure assuming a standard deviation of 12 based on our preliminary data from local facilities. These differences are considered clinically meaningful. We believe this hypothesized effect exists because of previous literature using these measures in clinical populations and from our pilot data.^{62,64}

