The original sample size analysis for the study used a closed solution formula for a *closed* cohort design, fixed sample size per cluster, and an underlying model with assumptions valid for a large number of clusters. The study is an *open* cohort design allowing participants to drop out of the study (move out of the facility) and new residents to come into the study as they move into the facilities. In addition, the number of clusters is small (only 8) and the number of residents per facility is variable. We conducted simulations to assess the power and Type I error rate of our study given the open cohort design, variability in sample size across facilities, and statistical analysis model that accounts for the small number of clusters. We found the estimated power to be 77-79% with $\alpha=0.025$ and 85-87% with $\alpha=0.05$ with minimal to no inflation in the Type I error rates (observed 0.025 to 0.033 for $\alpha=0.025$ and 0.045 to 0.058 for $\alpha=0.05$) assuming a drop out (churn rate) of 7.5% per period. These simulations were sent to the DSMB and approved prior to study start. Once the study began, the targeted sample size per facility (~65) was deemed not to be achievable due to lower than expected census and higher than expected resident decline to participate. Additional simulations showed that with 10 facilities, 5 steps (2 facilities per step), and 30 residents per facility, we achieved 85% power for the same hypothesized effect size and correlation parameters.

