9.4.7 SUB-GROUP ANALYSES

In an effort to ascertain whether the intervention is more or less effective for certain resident subgroups (**RQ-4, HT-1**), we will explore the following groups (**HT-2**):

(a) those who have different degrees of hearing loss at baseline (~84% expected to have some level of hearing loss) and those who do not;

H_1 The intervention provided by the Engage Model and measured by the HHIE and Satisfaction with Participation will have more impact on residents with hearing loss at baseline as compared to residents with no measured hearing loss.

H_0 The intervention provided by the Engage Model and measured by the HHIE and Satisfaction with Participation will not have a different impact on residents with hearing loss at baseline as compared to residents with no measured hearing loss.

(b) those who have different degrees of hearing loss and use a device (~18-32% of 84%; note these are estimates and the actual percent of device use will be used) compared to those who do not use a device but have different degrees of hearing loss;

H_1 The intervention provided by the Engage Model and measured by the HHIE and Satisfaction with Participation will have more impact on residents with hearing loss who do not use a hearing device at baseline as compared to residents with hearing loss who do use a hearing device.

H_0 The intervention provided by the Engage Model and measured by the HHIE and Satisfaction with Participation will not have a different impact on residents with hearing loss who do not use a hearing device at baseline compared to residents with hearing loss who do use a hearing device.

(c) those with high social participation at baseline (~50%) and those with lower social participation;

H_1 The intervention provided by the Engage Model and measured by Social Participation will have more impact for residents with low social participation at baseline compared to residents with normal or high social participation.

H_0 The intervention provided by the Engage Model and measured by Social Participation will not have a different impact for residents with low social participation at baseline compared to residents with normal or high social participation.

(d) those with high hearing-specific HRQoL (~50%) and those with lower hearing-specific HRQoL. Scores of 0-8 on the HHIE are “low” and 10-40 are “high” with 10% indicating a significant change.⁸³

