H_1 The intervention provided by the Engage Model and measured by HHIE will have more impact for residents with high hearing-specific HRQoL at baseline as compared to residents with hearing-specific HRQoL within normal limits.

H_0 The intervention provided by the Engage Model and measured by HHIE will not have a different impact for residents with high hearing-specific HRQoL at baseline as compared to residents with hearing-specific HRQoL within normal limits.

The individual hearing threshold data will allow us to stratify according to hearing levels. We will use the ASHA classification of degrees of hearing loss (normal -10 to 15; slight 16 to 25; mild 26 to 40; moderate 41 to 55; moderately severe 56 to 70; severe 71 to 90; profound >91 dB).⁸⁴ The number of individuals in the HHIE subgroups and hearing level subgroups cannot be adequately estimated and will be known when data collection are complete. We will explore the heterogeneity using interaction terms (**HT-3**) between the factor of interest and the intervention fixed effect. Regardless of the significance, we will estimate the treatment effect for each subgroup with corresponding 95% confidence intervals (**HT-2**).

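### The two primary outcomes are tested at a fixed 0.025 each but reported with 95% intervals; Holm would recover power at no Type I cost and reduce the mismatch (minor)

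*Combined protocol and SAP*

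**What the plan says.** Section 9.4.2 of the protocol covers both primary outcomes: satisfaction with social participation in all residents, and the HHIE in residents with measured hearing loss. It plans "A two-sided test $\alpha=0.025$ for each outcome", using a Wald t-test with small-sample correction. The preceding sentence says "We will estimate the mean difference and corresponding 95% confidence interval for the intervention effect". Section 9.2 uses the same 0.025 per outcome for the original sample size.

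Section 9.4.1 sets the general rule: "All tests will be two-sided and conducted at $\alpha=0.05$ and all confidence intervals calculated at 95% unless otherwise stated". Interval wording of the same kind appears for the secondary outcomes (9.4.3) and for subgroups (9.4.7: "we will estimate the treatment effect for each subgroup with corresponding 95% confidence intervals"), where no 0.025 test applies.

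The protocol does not say that the primary intervals are unadjusted for multiplicity, or how to read them beside the test. The one use of "unadjusted" in 9.4.2 is about covariates. Section 9.4.1 cites a full SAP dated October 6, 2021 as a separate document, which was not available for this review.

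**The concern.** A two-sided 0.025 test corresponds to a 97.5% interval. Beside a 95% interval there is a zone, 0.025 <= p < 0.05, in which the prespecified test fails and the reported interval excludes zero. A reader could take such an interval as a positive finding.

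The larger practical point is the testing rule. A fixed split of 0.025 and 0.025 spends the second half of the alpha on an outcome even after the other has been rejected. Holm's procedure reuses it. With two hypotheses that the investigators expect both to be false, the fixed split forgoes power, and it leaves more results in the zone of disagreement than necessary.

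**Working it through.** **1. The plan's own power figures.** Section 9.2 gives intracluster correlation 0.20, individual autocorrelation 0.5, cluster autocorrelation 0.9 and effect 0.3 SD. The standard error (SE) comes from generalised least squares with random effects for facility, facility by time, and resident. The documents state no degrees of freedom, so every df below is an assumption.

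- Original design (8 facilities, 65 residents each, 5 periods): SE 0.0925 SD. Power at 0.025 is 84.2% (normal) or 80.0% (26 df); the plan states 80%. With 7.5% churn and 26 df it is 78.9%; the plan's simulations gave 77-79%.
- Current design: the plan reports that with "30 residents per facility, we achieved 85% power for the same hypothesized effect size and correlation parameters". With 10 facilities, 6 periods and the 7.5% churn carried over as an assumption, SE is 0.0861 SD and power at 0.025 is 84.6% (20 df), 87.3% (44 df) or 89.3% (large df).
- HHIE: section 9.4.7 has "84% expected to have some level of hearing loss", so 0.84 x 30 = 25.2 residents per facility. SE is 0.0895 SD and power is 81.5%, 84.5% or 86.6% for the same df.

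So 85% per outcome at 0.025 is a fair working value for both outcomes.

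**2. Disagreement under the fixed split.** The normal critical values are 2.241 (0.025) and 1.960 (0.05). Power of 85% at 0.025 implies a mean z of 2.241 + 1.036 = 3.278. Power at 0.05 is then Phi(3.278 - 1.960) = 90.6%. The chance of disagreement per outcome is 90.6 - 85.0 = 5.6% (6.5% at 20 df). Under the null it is 5.0 - 2.5 = 2.5%.

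**3. Holm against the fixed split, both effects real, independent outcomes.** Write b = 0.0562 for the chance of falling in the zone.

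- Both rejected, fixed split: 0.85^2 = 0.723.
- Both rejected, Holm (both beyond 1.960, but not both in the zone): 0.9062^2 - 0.0562^2 = 0.8212 - 0.0032 = 0.818.
- Each outcome, Holm: 0.85 + 0.0562 x 0.85 = 0.898.
- At least one rejected, either rule: 1 - 0.15^2 = 0.978.
- At least one disagreement, fixed split: 1 - (1 - 0.0562)^2 = 0.109.
- At least one disagreement, Holm (neither beyond 2.241, at least one in the zone): 0.15^2 - 0.0938^2 = 0.0225 - 0.0088 = 0.014.

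**4. With correlated outcomes.** Bivariate normal simulation, 4,000,000 draws; the correlations are assumed.

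| Both effects real | rho 0 | rho 0.5 | rho 0.8 |
|---|---|---|---|
| Power for both, fixed | 0.723 | 0.758 | 0.791 |
| Power for both, Holm | 0.818 | 0.837 | 0.855 |
| Power per outcome, Holm (fixed 0.850) | 0.898 | 0.890 | 0.882 |
| At least one rejected, either rule | 0.977 | 0.942 | 0.909 |
| At least one disagreement, fixed | 0.109 | 0.107 | 0.103 |
| At least one disagreement, Holm | 0.014 | 0.028 | 0.039 |

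If only one effect is real, its power moves from 0.850 to 0.851-0.852. If neither is real, familywise error is 0.049, 0.046 and 0.040 under both rules.

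**5. Matching intervals if the split is kept.** The ratio of 97.5% to 95% half-widths is 2.241/1.960 = 1.144 (large df), 1.152 (44 df) and 1.162 (20 df). It would be about 1.19 at 9 df.

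**The case against.** The strongest reply is that nothing here is wrong. The 0.025 test is explicit in 9.2 and 9.4.2 and is the only stated decision rule. Section 9.4.1 makes 95% the default for intervals, and 9.4.2 repeats it. A 95% interval beside a 0.025 test is an acceptable convention, and the separate SAP may explain it. All of this stands. Labelling the intervals would, on its own, only fill in missing detail.

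A reader might go further and infer that 9.4.2 contradicts itself, that familywise error rises to nearly 0.10, or that the 95% level was carried over by mistake. The documents support none of these. Familywise error would reach 0.0975 (independent outcomes) only if significance were read from the 95% intervals, which the plan does not propose. The matching wording in other sections fits a deliberate uniform convention as well as an oversight. Nor does the plan claim joint coverage for its intervals.

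It can also be said that Holm is out of place, because it has no simple, exactly matching intervals. That is true, and it is a small cost. But Holm does not work against the purpose: it lets a second outcome with p below 0.05 be declared once the first has passed, so test and 95% interval then agree. Its advantage over the fixed split does not depend on the intervals at all.

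**Conclusion.** The point holds as a minor one. Type I control is unaffected. The cost of the fixed split is power: with both effects real, about 3 to 5 percentage points per outcome and 6 to 10 points for both together. The chance that at least one test and its 95% interval disagree is about 10-11% under the fixed split and 1-4% under Holm. If only one effect is real, the power gain is 0.1-0.2 points. Holm does not change the chance of winning at least one outcome.

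These figures rest on 85% power per outcome at 0.025, normal critical values and an assumed correlation of 0 to 0.8. The protocol gives no alpha for its 85%. A reader might infer that it was computed at 0.025, but the close match in the working (84.6%) needs an assumed 20 df, so that is not established. Nor can it be concluded that the plan as a whole is silent on the intervals: the finding covers the available text only, and the separate SAP may address it.

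**What to change.** Before comparative data are seen, replace the fixed split in 9.4.2 with Holm: test the smaller of the two primary p-values at two-sided 0.025 and, if it is significant, the other at 0.05. Keep the 95% intervals, label them unadjusted for multiplicity, and state that the Holm decision governs. Leave the secondary and subgroup intervals at 95%. Bring the separate SAP into line.

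The cost is a few lines of text. No data, model or sample size changes, every rejection under the current rule is kept, and 9.4.6 plans no interim analysis that would complicate the change. The one drawback is the lack of simple, exactly matching intervals.

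If the fixed split is kept, report 97.5% intervals for the two primary outcomes. They are about 14-16% wider at 20 df or more. If 95% intervals are shown as well, label them unadjusted and state that the 0.025 test decides.

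### Testing each primary outcome at a fixed 0.025 is valid, but Holm would add about 4 to 5 points of power per outcome when both effects are real, at the same nominal 5% family-wise error

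*Combined protocol and SAP*

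**What the plan says.** Section 9.1 states a separate hypothesis for each of two primary outcomes. Section 9.4.2 tests them with "A two-sided test $\alpha=0.025$ for each outcome using a Wald t-test", and section 9.2 sizes the trial on the same basis: "two-sided, $\alpha=0.025$ for each outcome". No step-down, ordered or alpha-recycling rule appears in the text reviewed. Section 9.4.1 refers to a separate full SAP dated October 6, 2021, which was not supplied.

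The design target was 80% power "to detect the hypothesized effect size of 0.3 for either primary outcome". For the original 8-facility design, section 9.2 then reports simulated power of 77-79% at 0.025 and 85-87% at 0.05, with "minimal to no inflation in the Type I error rates (observed 0.025 to 0.033" at 0.025, and 0.045 to 0.058 at 0.05). For the current 10-facility design it says that with "30 residents per facility, we achieved 85% power for the same hypothesized effect size"; the alpha is not restated there.

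**The concern.** A fixed 0.025 for each of two outcomes is a Bonferroni split. It never uses the 0.025 that becomes free once one outcome has been confirmed. If one outcome passes 0.025 and the other has p between 0.025 and 0.05, the plan must call the second not significant. Holm would confirm it at the same nominal family-wise error. The trial has two aims, each of interest in its own right, and enrolment per facility fell short of plan, so power that needs no extra residents is worth having. What is at stake is confirmation of the second outcome. The chance of confirming at least one does not change.

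**Working it through.** **Inputs.** From section 9.2: two-sided 0.025 per outcome; effect size 0.3; intracluster correlation 0.20; cluster autocorrelation 0.9; individual autocorrelation 0.5; churn 7.5% per period; 8 facilities of 65 over 5 periods (original) and 10 facilities of 30 with 5 steps (current, so 6 periods). Assumed: the correlation r between the two test statistics. It is not in the documents, and it depends on facility and facility-by-time components as well as on residents. I range it from 0 to 0.9.

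**1. Reproducing the plan's power.** Generalised least squares with random facility, facility-by-time and resident effects, 8 x 65: SE 0.0925, noncentrality 0.3/0.0925 = 3.24. A normal test gives 84.2%. A t test on 40 - 8 - 5 = 27 df gives 80.2%, which matches the stated 80%. With 7.5% churn the t test gives 79.1% at 0.025 and 87.0% at 0.05, close to the simulated 77-79% and 85-87%.

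**2. Which alpha lies behind the 85%?** For 10 x 30 with churn and 60 - 10 - 6 = 44 df, I get 87.3% at 0.025 and 92.6% at 0.05. The stated 85% is much nearer the 0.025 figure, so I use 85% at 0.025. If it was at 0.05, power at 0.025 would be about 77.5% and Holm's gain larger (4.8 to 5.8 points for r = 0.5 to 0).

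**3. Holm's gain.** For outcome A with partner B:

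Holm power(A) = P(pA <= 0.025) + P(0.025 < pA <= 0.05 and pB <= 0.025).

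Critical values are 2.241 and 1.960. 85% power at 0.025 means noncentrality 2.241 + 1.036 = 3.278 (from unrounded values), so power at 0.05 is 90.62%. The band between the two levels therefore holds 5.62 points. At r = 0 the gain is 0.85 x 5.62 = 4.8 points. For other r, bivariate-normal integration gives:

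| r | Gain per outcome (points) | Both confirmed, fixed | Both confirmed, Holm | At least one, either rule |
|---|---|---|---|---|
| 0 | 4.8 | 0.7225 | 0.8181 | 0.978 |
| 0.3 | 4.3 | 0.7415 | 0.8274 | 0.959 |
| 0.5 | 3.9 | 0.7577 | 0.8363 | 0.942 |
| 0.7 | 3.5 | 0.7782 | 0.8479 | 0.922 |
| 0.9 | 2.7 | 0.8084 | 0.8630 | 0.892 |

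With t statistics on 44 df the per-outcome gain is 5.1 (r = 0) and 4.3 (r = 0.5).

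**4. Unequal outcomes.**
- Partner at 50% power: the 85% outcome gains 0.50 x 5.62 = 2.8 points at r = 0 and 1.4 at r = 0.5. The weaker outcome gains 9.4 to 9.6.
- Partner null: the 85% outcome gains about 0.15 points.
- Hearing outcome analysed only in residents with hearing loss (84% in the pilot work of section 4.3, so 0.84 x 30 = 25.2 per facility): its power is about 82%. It gains 4.7 to 5.5 points and the other outcome 3.6 to 4.6 (r = 0.5 to 0).

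**5. Error.**
- Both null: each rule makes an error exactly when the smaller p-value is at or below 0.025, so family-wise error is identical. If independent, it is 1 - 0.975^2 = 4.94% nominally. At the upper simulated rate of 0.033 it is 1 - 0.967^2 = 6.5%.
- One null, partner at 85% power, r = 0: the fixed split gives 2.5%. Holm gives 0.025 + 0.85 x 0.025 = 4.6% (4.4% at r = 0.5).
- The same case with the upper rates simulated for 8 facilities: 3.3% fixed, against 0.85 x 0.058 + 0.15 x 0.033 = 5.4% under Holm. With the lower rates: 2.5% against 0.85 x 0.045 + 0.15 x 0.025 = 4.2%.

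**The case against.** The fixed split is standard, consistent between sections 9.2 and 9.4.2, and evidently deliberate. The design target was 80% and the current design reports 85%, so the plan does not need the extra power. Nothing makes success depend on both outcomes. Holm also nearly doubles the error on a single true null, in a trial that already reports some small-sample inflation. The change would relax the decision rule after enrolment began, while section 6.3 says the research team is not blinded. The 4 to 5 points are the favourable case and rest on an undocumented correlation.

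All of this stands as fact. It makes the change optional, but it does not remove the advantage: at the same nominal bound, Holm never rejects less.

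Three stronger readings are tempting and not supported.
- A reader might infer that the split is an error or fails to control error. It is nominally valid.
- A reader might infer that the trial is underpowered, or that it must win on both outcomes. The stated power meets the target, and the phrase about either outcome in section 9.2 most naturally describes power per outcome, not a rule for success.
- A reader might take the 95% intervals in section 9.4.2 ("We will estimate the mean difference and corresponding 95% confidence interval for the intervention effect") beside a 0.025 test as part of this fault. That mismatch is a separate reporting point. Holm removes only part of it, whereas 97.5% intervals under the fixed split would remove all of it. The unstated alpha behind the 85% is likewise separate.

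**Conclusion.** The fixed 0.025 per outcome is valid, and Holm dominates it on power at the same nominal 5% family-wise error. With both outcomes at 85% power, the gain is about 4 to 5 points per outcome for r between 0.5 and 0 (2.7 at r = 0.9), and 8 to 10 points in the chance of confirming both. The chance of at least one success is unchanged. The gain for an 85% outcome shrinks to 1.4-2.8 points beside a 50% partner and to about 0.15 beside a null one. This rests on the assumed r, on reading the 85% as power at 0.025, and on the separate SAP having no step-down. The arithmetic is firm, but confidence in the point as a whole is moderate because that SAP was not seen. It is a low-cost improvement the sponsor should consider, not a correction it must make.

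**What to change.** 1. Check the separate SAP. If it already has a step-down, it conflicts with section 9.4.2 and the two must be reconciled.
2. If it has none, amend section 9.4.2 and the SAP: test the smaller of the two primary p-values at two-sided 0.025; if significant, test the other at 0.05; otherwise stop. Keep 0.025 as the sample-size basis.
3. Date the amendment and record that no outcome comparison by condition has been seen. This matters because the research team is unblinded, although section 6.3 blinds the data core analysts and section 9.4.6 plans no interim analysis. If that record cannot honestly be made, keep the fixed split.
4. If the 10-facility simulation is rerun as a check, use the case of one true null and one real effect, with the acceptable error limit fixed beforehand. The both-null case cannot separate the two rules. The limit matters: the 8-facility rates put Holm at 4.2% to 5.4% in the one-null case. The result can go to the DSMB as before ("These simulations were sent to the DSMB and approved prior to study start").

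**Cost.** No more residents or data. Prior funder agreement and IRB approval are needed under the Statement of Compliance. The statistical price is higher error on a single true null (2.5% to about 4.4-4.6% nominally) and the loss of the simple matching 97.5% intervals that the fixed split allows. There is also a credibility price in relaxing the rule after enrolment began, which the dated record limits.
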